14. MEASUREMENT OF EFFECT

Definitions: Response and progression will be assessed according to modified International Working Group (IWG) 2006 criteria³⁴ (Appendix B).

15. STATISTICAL CONSIDERATIONS

1. Study Design

This study will be a multi-institution, open-label, phase Ib/II clinical trial conducted in 2 parts: a Phase 1b part followed by a Simon's two-stage Phase 2 design. The study will assess the safety and efficacy of APR-246 in combination with azacitidine for the treatment of *TP53* mutant myeloid neoplasms. All patients will have pre-screening NGS on peripheral blood (PB) or bone marrow (BM) samples to determine *TP53* mutational status and therefore eligibility to participate in this study. A PB sample will be obtained prior to treatment for NGS by the central laboratory to evaluate baseline VAF and for serial analysis. The initial Phase 1b part will evaluate APR-246 administered with azacitidine. Cohorts of at least 3 evaluable patients will be enrolled using a modified 3 + 3 design. The MTD is defined as the dose level below which DLT is manifested in $\geq 33\%$ of the patients or at dose level 1 if DLT is manifested in $< 33\%$ of the patients.

Following completion of the Dose Finding Phase, we will conduct a dose expansion, whereby patients will be treated with APR-246 administered at the MTD with azacitidine on a 28 day cycle utilizing the same dosing schedule as in Phase 1b. All patients who complete at least one treatment cycle of APR-246 and azacitidine and who have at least one post-treatment clinical response assessment will be considered eligible for the efficacy-evaluable population and will be summarized for all efficacy variables. Patients who fail to complete one treatment cycle will also be considered efficacy-evaluable if they show clear evidence of clinically significant disease progression. Patients who are not efficacy-evaluable will be replaced. A Simon's two-stage minimax design will be applied, as follows:

Stage 1: Enroll a total of 24 evaluable patients at the MTD (including patients who were enrolled during the Phase 1 part of the study). If less than 6 of 24 patients achieve CR, then the study will be terminated early with the conclusion that the regimen does not warrant further investigation. If 6 or more patients achieve CR, then enrollment will be permitted to continue to Stage 2.

Stage 2: Enroll 21 more evaluable patients for a total of 45. If less than 14 of 45 patients achieve CR, then there is insufficient evidence to support continued study of this treatment. If at least 14 of 45 patients achieve CR, then there is sufficient evidence to support further study of APR-246 in combination with azacitidine in Phase 3. Up to 39 additional evaluable patients will be treated at the level of the MTD in the

Phase 2 portion of the trial.

This rule has the following operating characteristics: 90% power, with $\alpha=0.05$ under the null hypothesis that the proportion of patients achieving CR is $\leq 20\%$ versus the alternative hypothesis that it is $\geq 40\%$. This design has a probability of early termination equal to 0.66 if the true CR rate is 20%.

2. Statistical Analysis Methods

Demographic and clinical variables for the study patients will be summarized using descriptive statistics (mean, standard deviation, median, inter-quartile range, range, frequency counts and percentages). Safety and efficacy data will be analyzed overall as well as separately for each dose cohort when appropriate.

3. Safety Analysis

This analysis will include all subjects who have received any protocol treatment, regardless of patient eligibility. The number (%) of subjects with adverse events, serious adverse events, and adverse events leading to treatment discontinuation will be reported. Adverse events summary will be reported by type and severity. Laboratory parameters will also be summarized using descriptive statistics.

4. Efficacy Analysis: ITT

This analysis will include all subjects who have received any protocol treatment, regardless of patient eligibility or duration of treatment. Those who have no response assessment data due to reasons such as drop out of the study, withdrawal consent, or lost to follow-up will be treated as non-responders for various response evaluations. The proportion of subjects achieving the primary endpoint will be summarized. A 95% exact binomial confidence interval of the proportion will also be provided for all participants treated at the MTD. In addition, a second analysis of evaluable subjects will be performed. Evaluable subjects are defined as those who complete at least 3 cycles of therapy and complete the first on treatment bone marrow biopsy and aspirate to evaluate study drug response.

Analyses of the following secondary endpoints will be performed as well:

- i. Duration of response defined as the time between achieving response and progression of disease.
- ii. OS at 8 months
- iii. Proportion of subjects achieving hematological improvement (HI), partial response (PR), complete response (CR), and/or marrow CR (mCR) by the IWG 2006 criteria (see appendix B)
- iv. Proportion of subjects who obtain a response as defined by IWG 2006 criteria with a baseline *TP53* VAF $\geq 20\%$ versus $< 20\%$ or high versus low nuclear p53 protein expression

- v. Correlation of *TP53* VAF with nuclear p53 protein expression as determined by IHC
- vi. Proportion of subjects who achieve $\geq 50\%$ reduction in *TP53* VAF.
- vii. Progression free survival (PFS) and OS in clonal responders ($\geq 50\%$ reduction in *TP53* VAF) versus non-responders
- viii. Profile expression of genes related to p53-mediated signal transduction before and after APR-246 treatment
- ix. Profile ROS production before and after APR-246 treatment
- x. AML transformation according to World Health Organization (WHO) criteria
- xi. OS
- xii. LFS
- xiii. Determine recurrent gene mutations in *ASXL1*, *BCOR*, *BRAF*, *CALR*, *CBL*, *CEBPA*, *CSF3R*, *DNMT3A*, *ETV6*, *EZH2*, *GATA2*, *GNAS*, *IDH1*, *IDH2*, *JAK2*, *KIT*, *KRAS*, *MPL*, *NF1*, *NPM1*, *NRAS*, *PDGFRA*, *PDGFRB*, *PHF6*, *PTPN11*, *RAD21*, *RUNX1*, *SETBP1*, *SF3B1*, *SMC1A*, *SMC3*, *SRSF2*, *STAG2*, *STAT3*, *STAT5b*, *TET2*, *TP53*, *U2AF1*, *WT1*, and *ZRSR2* at study entry and serially throughout treatment to assess changes in somatic mutation landscape.

Preliminary data on the above endpoints will prove to be very useful for further investigation of this protocol's treatment. Such data will be summarized appropriately in an exploratory fashion. Both point estimates and 95% confidence intervals will be reported, if feasible. Time-to-event endpoints such as OS and LFS will be summarized using the Kaplan-Meier product-limit method.

16. Laboratory Correlates

Unless otherwise specified, all laboratory correlates will be performed in the laboratory of [name] or at Genoptix medical laboratory.

1. Mutation analyses

Genoptix medical laboratory ([name]) will be the central laboratory for this study regarding molecular profiling. All patients will undergo baseline NGS for confirmation of *TP53* mutation, baseline *TP53* VAF, and identification of additional somatic mutations. These analyses will not impact enrollment into the clinical trial. Importantly, there will be serial evaluation following cycle 3 and cycle 6 where NGS will be repeated to evaluate for clonal reduction of *TP53* VAF as well as changes in the underlying mutational architecture of these patients. These analyses will be utilized for secondary endpoints #4-7. **For correlative genomic studies that will be performed at Genoptix medical laboratory, 2-3 mL of peripheral blood will be obtained in a standard Vacutainer tube with EDTA (purple top) as anticoagulant. If *TP53* mutation is only present on BM analysis at screening, serial NGS myeloid panel**

can be performed on bone marrow MNC. A FedEx shipping label will be included in the shipper box with a research specific requisition. Recurrent gene mutations of *ASXL1*, *BCOR*, *BRAF*, *CALR*, *CBL*, *CEBPA*, *CSF3R*, *DNMT3A*, *ETV6*, *EZH2*, *GATA2*, *GNAS*, *IDH1*, *IDH2*, *JAK2*, *KIT*, *KRAS*, *MPL*, *NF1*, *NPM1*, *NRAS*, *PDGFRA*, *PDGFRB*, *PHF6*, *PTPN11*, *RAD21*, *RUNX1*, *SETBP1*, *SF3B1*, *SMC1A*, *SMC3*, *SRSF2*, *STAG2*, *STAT3*, *STAT5b*, *TET2*, *TP53*, *U2AF1*, *WT1*, and *ZRSR2* will be evaluated at each NGS analysis. DNA and RNA will be isolated from BM-MNC by the Ficoll method following cycle 3 and cycle 6 and stored in the laboratory of [name]. In patients who become negative for *TP53* mutation by NGS (VAF sensitivity for this assay is 1% in patients with previously identified variants), we will perform PCR-based barcoding or digital droplet PCR to identify rare variants in an effort to determine the depth of remission induced by treatment with APR-246 and azacitidine.

2. Immunohistochemistry for p53 expression

BM core biopsies will be centrally evaluated at Moffitt Cancer center by [name] to evaluate for p53 protein expression as a biomarker of response, correlation with *TP53* VAF, and serially over the course of treatment (secondary endpoints # 4-5). Three sections from each core biopsy will be obtained at baseline and following cycle 3 and 6 of therapy. To evaluate for p53 protein expression, p53 IHC will be performed using a standard protocol (p53 antibody, clone Bp53-11, Ventana Medical Systems, Tucson, AZ, USA). Nuclear p53 expression will be assessed quantitatively by percent p53 positivity and semi-quantitatively with an IHC score of stain intensity (0, 1+, 2+, and 3+) multiplied by percent positive hematopoietic cells.

Shipping

Bone marrow core biopsies will be shipped to the below address.

H. Lee Moffitt Cancer Center

[name]

[name]

[name]

[contact]

3. *In vivo* evaluation of APR-246

As the primary mechanism of action of APR-246 is restoration of wild-type function of p53, we will utilize the lead in phase of APR-246 monotherapy to assess the activation of downstream targets of p53. An additional 20ml of bone marrow aspirate will be obtained in purple EDTA tubes at the pre-study bone marrow (prior to Cycle #1) and on day -10 following four days of APR-246 as well as at disease assessments (following cycle 3 and cycle 6; see study calendar). Utilizing the bone marrow aspirates, the mononuclear

cells will be collected with isolation of DNA and RNA as previously described and stored in the laboratory of [name]. Evaluation of p53-mediated signal transduction will be analyzed using Qiagen human p53 Signaling Pathway RT² Profiler PCR Array (secondary endpoint #8). As production of ROS leading to DNA damage is an additional mechanism of action of APR-246, we will evaluate for ROS production before and after APR-246 monotherapy via flow cytometry (CellROX® Deep Red Reagent, Life Technologies; secondary endpoint #9).

i. Shipping

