[figure not shown]
This study will be a multi-institution, open-label, phase Ib/II clinical trial conducted in 2 parts: a Phase 1b part followed by a Simon’s two-stage Phase 2 design. The study will assess the safety and efficacy of APR-246 in combination with azacitidine for the treatment of *TP53* mutant myeloid neoplasms. All patients will have pre-screening NGS on peripheral blood (PB) or bone marrow (BM) samples to determine *TP53* mutational status and therefore eligibility to participate in this study. A PB sample will be obtained prior to treatment for NGS by the central laboratory to evaluate baseline *TP53* VAF and for serial analysis.

Evaluable: Patients will be evaluable for inclusion in the Phase 1b and Phase 2 portions of the study if they receive at least one dose of protocol therapy.

Phase 1b Part:

The initial Phase 1b part will evaluate APR-246 administered with azacitidine (see Figure 1). Cohorts of at least 3 evaluable patients will be enrolled using a modified 3 + 3 design.

Figure 1

Patients will receive intravenous infusions of APR-246 as a lead-in phase on days -14 to -11 starting at Dose Level 1 (see Table 1) prior to starting cycle #1 of combination therapy with azacitidine (see Figure 1). Combination therapy will consist of APR-246 on days 1-4 and azacitidine on days 4-10 (or days 4-5 and 8-12) of a 28 day cycle. Patients will be followed for at least 6 weeks (lead in phase + cycle 1) before the safety of each cohort can be fully assessed and decisions made for dose escalation in the next cohort. The MTD is defined as the dose level below which DLT is manifested in $\geq 33\%$ of the patients or at dose level 3 if DLT is manifested in $< 33\%$ of the patients.

Table 1. Dose Levels for Treatment Part 1: APR-246+Azacitidine

Dose Level	APR-246 (mg/kg lean body weight (LBW))	Azacitidine (mg/m ²)
1 (Starting dose)	50	75
2	75	75
3	100	75

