Phase 1b, patients (n = 6 to approximately 18) will receive APR-246 in combination with azacitidine. Cohorts of at least 3 evaluable patients will be enrolled using a modified 3+3 design. If no DLT is observed in a cohort, the subsequent patient group will be enrolled at the next planned dose level. If a DLT is observed in 1 of 3 patients in a cohort at any dose level, then up to 3 additional patients will be enrolled at that dose level. If only 1 DLT occurs in the 6 patients treated at that dose level, the subsequent patient group will be enrolled at the next planned dose level. If 2 of 6 patients in a cohort have a DLT, dose escalation ceases and the MTD is the previous dose level. If only 3 patients were treated at the MTD, an additional 3 patients will be included in the cohort and if only 0 or 1 DLT occur in the 6 patients treated at that dose level, the MTD will be defined and we will proceed to Phase 2.

[figure not shown]
Phase 2: Simon’s two-stage minimax design:

Following completion of the Dose Finding Phase, we will conduct a dose expansion, whereby patients will be treated with APR-246 administered at the MTD with azacitidine on a 28 day cycle utilizing the same dosing schedule as in Phase 1b with the exception of no lead in phase (i.e. patients will start at day 1 of combination therapy with APR-246 on days 1-4 and azacitidine on days 4-10 (or days 4-5 and 8-12) of a 28 day cycle, see Figure 1). If dose level 3 (i.e. 100mg/kg LBW) is the RP2D based on the phase 1b part of the trial, the dosing will be changed to an equivalent fixed dose regimen of 4500mg/patient (see below). All patients who complete at least one treatment cycle of APR-246 and azacitidine and who have at least one post-treatment clinical response assessment will be considered eligible for the efficacy-evaluable population and will be summarized for all efficacy variables. Patients who fail to complete one treatment cycle will also be considered efficacy-evaluable if they show clear evidence of clinically significant disease progression. Patients who are not efficacy-evaluable will be replaced. A Simon’s two-stage minimax design will be applied, as follows:

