Stage 1: Enroll a total of 24 evaluable patients at the MTD (including patients who were enrolled during the Phase 1 part of the study). If less than 6 of 24 patients achieve CR, then the study will be terminated early with the conclusion that the regimen does not warrant further investigation. If 6 or more patients achieve CR, then enrollment will be permitted to continue to Stage 2.

Stage 2: Enroll 21 more evaluable patients for a total of 45. If less than 14 of 45 patients achieve CR, then there is insufficient evidence to support continued study of this treatment. If at least 14 of 45 patients achieve CR, then there is sufficient evidence to support further study of APR-246 in combination with azacitidine in Phase 3. Up to 39 additional evaluable patients will be treated at the level of the MTD in the Phase 2 portion of the trial. The maximum total accrual is 51 patients. Disease assessments will occur following 3 cycles of therapy (Figure 3).

Figure 3. Phase 2 Schema

This rule has the following operating characteristics: 90% power, with alpha=0.05 under the null hypothesis that the proportion of patients achieving CR is $\leq 20\%$ versus the alternative hypothesis that it is $\geq 40\%$. This design has a probability of early termination equal to 0.66 if the true CR rate is 20%.

Number of Patients Planned:

The number of patients enrolled will depend on the number of dose levels evaluated before reaching DLT. Three to 6 evaluable patients will be entered per dose level. It is anticipated that up to 18 evaluable patients can be treated in the Phase 1b portion of the study. Up to 39 additional evaluable patients will be treated at the level of the MTD in the Phase 2 portion of the trial. The maximum total accrual is 51 patients.

Analyses to address study objectives

To address the primary objective for Phase 1b, we will apply the 3+3 design above.

To address the primary objective for Phase 2, we will apply the Simon's two-stage minimax design above.

Analysis of the following secondary endpoints will be of exploratory nature:

Duration of response defined as the time between achieving response and progression of disease.

OS at 8 months

Proportion of subjects achieving hematological improvement (HI), partial response, complete response (CR), and/or marrow CR (mCR) by the IWG 2006 criteria (see appendix B)

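### The 6/24 and 14/45 CR rules do not say which of three 'evaluable' sets they count, and the replacement promise and the target of 45 do not fit the cap of 51 on most escalation paths

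*Combined protocol and SAP*

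**What the plan says.** The stage rules in the synopsis, Section 6 and Section 15.1 call for 24 evaluable patients at the MTD and then 21 more, without saying which definition of evaluable applies. Three definitions are given:

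- **One dose.** The synopsis (Statistics, Evaluable) treats patients as "evaluable for inclusion in the Phase 1b and Phase 2 portions of the study if they receive at least one dose" of protocol therapy.
- **Efficacy-evaluable.** The synopsis (Phase 2) and Section 15.1 admit "All patients who complete at least one treatment cycle of APR-246 and azacitidine and who have at least one post-treatment clinical response assessment". They add an exception: "Patients who fail to complete one treatment cycle will also be considered efficacy-evaluable if they show clear evidence of clinically significant disease progression". Then: "Patients who are not efficacy-evaluable will be replaced". The Simon rules follow directly.
- **Three cycles.** Section 15.4, for a second analysis: "Evaluable subjects are defined as those who complete at least 3 cycles of therapy and complete the first on treatment bone marrow biopsy" and aspirate.

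Section 15.4 also summarises the primary endpoint in all treated patients: "This analysis will include all subjects who have received any protocol treatment, regardless of patient eligibility or duration of treatment". Those without response data because of dropout, withdrawn consent or being "lost to follow-up will be treated as non-responders for various response evaluations".

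The synopsis (Treatment plan) limits the trial to 51 treated patients. Under Number of Patients Planned it says "It is anticipated that up to 18 evaluable patients can be treated in the Phase 1b portion of the study", with up to 39 more at the MTD.

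**The concern.** The go/no-go decision needs a fixed denominator. If the efficacy-evaluable set governs, a treated patient who stops for toxicity or withdraws before any assessment, without clear progression, is replaced in the decision count. The same patient is a failure in the CR rate reported beside it. The group is not confined to cycle 1, because planned disease assessment comes after cycle 3. Section 13 asks early stoppers for an end-of-treatment assessment, which keeps some of them in the set, but tests that are declined or not feasible are not a deviation. Appendix B classes a death during treatment as failure, and the plan does not say whether such a death counts as an assessment.

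The trial is open-label and single-arm, and its result decides whether a Phase 3 study is supported. The denominator should therefore not be open to choice after CR counts are known. The stated alpha and power apply to whichever set is counted, and only if 45 patients are counted.

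**Working it through.** **1. The plan's own figures.** Inputs from Section 15.1: null CR rate 20%, alternative 40%, stop at 5 or fewer of 24, go at 14 or more of 45. With X1 ~ Bin(24, p),

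P(go) = sum over x = 6 to 24 of P(X1 = x) × P[Bin(21, p) ≥ 14 − x].

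- p = 0.20: P(go) = 0.0483; early termination P(X1 ≤ 5) = 0.656.
- p = 0.40: P(go) = 0.9001.

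The stated design (alpha 0.05, power 90%, early termination 0.66) is reproduced.

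**2. Places at the MTD under the cap.** Places = 51 − m, where m is the number treated at other levels. A cohort has at least 3 patients, and up to 3 more may be added, so a level can close at 3, 4, 5 or 6.

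| m | Places at MTD | Replacements if 45 are to be counted |
|---|---|---|
| 3 | 48 | 3 |
| 4 | 47 | 2 |
| 5 | 46 | 1 |
| 6 | 45 | 0 |
| 7 to 12 | 44 to 39 | 45 not reachable |

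Fewer than 6 elsewhere requires that only one other level was treated, so level 1 is the MTD and level 2 the other level. If dose level 3 is the RP2D, levels 1 and 2 use at least 3 + 3 = 6 places, and none is left for replacement. The separate maxima sum to 18 + 39 = 57, so both cannot be reached under 51.

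**3. False-go with k replacements.** The documents give no exclusion rate. Assume that excluded patients are never in CR and that 20% is the rate among all treated. The CR rate in the 45 counted is then 0.20 × (45 + k)/45.

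| k | CR rate in counted set | P(go) |
|---|---|---|
| 0 | 0.2000 | 4.8% |
| 1 | 0.2044 | 5.7% |
| 2 | 0.2089 | 6.6% |
| 3 | 0.2133 | 7.6% |

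If excluded patients instead have a 10% CR rate, k = 3 gives (48 × 0.20 − 3 × 0.10)/45 = 0.2067 and P(go) = 6.1%.

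**4. Only 45 places, k excluded and not replaced.** The counted n is 45 − k, the rate is 0.20 × 45/(45 − k), and the boundary stays at 14. For k = 1, 2 or 3, P(go) is about 4.9% each time.

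**5. Stage 1, where the cap does not bind.** With an assumed share d excluded, the counted rate under the null is 0.20/(1 − d). Early termination falls from 0.66 to 0.61 (d = 5%) or 0.55 (d = 10%).

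**6. Fewer than 45 counted.** Here 20% and 40% are the rates in the counted set, and the 6/24 first stage is kept.

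| n | Boundary | Alpha | Power |
|---|---|---|---|
| 44 | 14 | 4.11% | 88.4% |
| 43 | 14 | 3.46% | 86.5% |
| 42 | 14 | 2.87% | 84.2% |
| 41 | 13 | 4.94% | 88.3% |
| 40 | 13 | 4.15% | 86.2% |
| 39 | 13 | 3.45% | 83.8% |

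A boundary of 13 at n = 42 would give alpha 5.8%. Keeping 14 at n = 39 would give 1.5% and 75% power, which gives up power needlessly.

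**The case against.** The strongest reply is that the set is clear enough. The efficacy-evaluable definition, the replacement sentence and the Simon rules are consecutive. The three-cycle definition is expressly for a second analysis, and the one-dose definition concerns inclusion in the study portions. This largely stands, and a reader who infers that the governing set cannot be guessed goes too far. But the rules use the bare word, and the one-dose definition uses that same word and expressly covers Phase 2.

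A reader might also infer that replacement contradicts Section 15.4. It does not: replacing patients in a decision count while reporting an all-treated rate is compatible, and 15.4 does not apply the decision rule. What remains is that the decision set is not fixed and, on the natural reading, differs from the set in 15.4.

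Likewise, 18 and 39 are each worded as upper limits and 51 as a joint ceiling, so a sum of 57 is not by itself an error. It does need reconciling, because the plan relies on 45 at the MTD.

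Finally, naming all treated patients as the decision set is partly a design preference, and it costs power if the 40% was meant among assessed patients.

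**Conclusion.** The point holds as a should-fix matter of definition and feasibility. The rules do not name their set, and the natural choice is not the set used in Section 15.4. The cap leaves at most 3 replacement places, and only when 3 to 5 patients were treated elsewhere. It leaves none when level 3 is the RP2D, and it puts 45 at the MTD out of reach once more than 6 are treated elsewhere. On those last paths the stated 90% power is not delivered, and the plan gives no boundary.

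The documents do not support a claim of serious alpha inflation. Under the least favourable assumption examined the false-go risk reaches 7.6%, and it stays near 4.9% when only 45 can be treated. There is no inflation if exclusion is unrelated to CR or if the one-dose definition governs. The exclusion rates are assumptions. The Simon arithmetic itself is correct.

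**What to change.** In the synopsis, Section 6 and Section 15.1, name one set for both rules. The preferred choice is the first 24 and first 45 patients given at least one dose at the MTD. Count anyone without a response assessment, including a patient who dies before assessment, as not in CR, and do not replace patients in the decision count. Keep one other 'evaluable' definition as a labelled sensitivity analysis with no decision role.

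If the sponsor prefers the efficacy-evaluable set, say so in the rules and report the all-treated CR count beside the decision. That removes the ambiguity but leaves the replacement sentence in conflict with the cap.

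Either way, reconcile 51 with 45 at the MTD, with 18 + 39 and with the replacement sentence. State that 90% power holds only if 45 are counted. Give the boundary for smaller n, with exact alpha and power as tabulated: 14 at 42 to 44, 13 at 39 to 41. The places left at the MTD are known once escalation ends, so the planned n and its boundary can be fixed then.

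The cost is wording, with no extra patients. The downside of the preferred set arises if 40% was meant among evaluable patients. The all-treated rate is then 0.40 × 45/(45 + k), and power is 88%, 86% or 83% with 1 in 46, 2 in 47 or 3 in 48 unassessed. At an assumed 5% or 10% unassessed (rates 0.38 and 0.36) it is 85% or 77.5%.
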